2.2 Secondary estimands

Not applicable.

3 Study design

This study is an open-label, multi-center, prospective eighteen-month study in a minimum of

118 MS patients with early RRMS (defined as within 6 months of diagnosis of clinically

definite RRMS) and who are disease modifying therapy (DMT) treatment naïve. RRMS patients will be benchmarked against age- and sex-matched healthy controls (n=50) for select secondary [REDACTED]. A screening period of 4 weeks will be used to assess eligibility and the assessment to address the primary objective will be performed at the end of the maintenance period (Month 18). There will be one interim analysis after the last participant completes his/her Month 18 (primary analysis time point) visit. Participants who complete the treatment period or who prematurely discontinue study drug and the study, and do not continue on any MS DMT, will undergo a safety evaluation 100 days following last dose of study treatment (captured only in source documents and only for ofatumumab treated participants), and will be discharged from the study if they choose to not be included in the optional extension portion of the trial for an additional 12 months (up to 30 months total in trial). Healthy control participants will not have a safety evaluation post end of study. Additional efficacy and safety assessments will be evaluated during the optional open-label extension to further elucidate the long-term clinical and radiological effects of ofatumumab (Figure 3-1). Of note, MRI data will be re-baselined at month 6 to account for treatment-related pseudo atrophy.

[figure not shown]
Eligible participants with RRMS will receive ofatumumab 20mg subcutaneous doses at Baseline/Week 0 (Day 1), followed by Week 1 (Day 7), Week 2 (Day 14) and then every month thereafter, beginning at Week 4 (Month 1) until Month 18 (see Figure 3-1). Additional efficacy and safety assessments will be evaluated up to 30 months, necessitating ofatumumab monotherapy over the course of up to 30 months. Ofatumumab will be administered according to the United States Prescribing Information (USPI). RRMS patients must remain on ofatumumab monotherapy to remain in the trial, with no DMT switching or combination DMT therapy allowed. Healthy controls will not be given a therapy.

Assessments will be performed per the assessment schedule found in Table 8-1.

Figure 3-1 Study design

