12.4.1 Definition of primary endpoint(s)

The primary endpoint will be NEDA-3 (Relapse-free, 3-month clinical disability progression-free, MRI activity-free) in Months 6 to 18 (yes/no).

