12.5 Analysis supporting secondary objectives

12.5.1 Efficacy endpoint(s)

For all efficacy analyses, the FAS will be used. The healthy control set will be used if applicable.

Descriptive statistics will be provided for the following variables:

- Number of relapses during the study
- 3-month disability worsening-free (yes/no) during the study
- NEDA clinical in Months 6 to 18 (yes/no)
- NEDA radiological in Months 6 to 18 (yes/no)
- Change from Baseline in conventional MRI metrics (Gd+ lesion number, new Gd+ lesion number, Gd+ lesion volume, T2 lesion number (Baseline), New/enlarging T2 lesion number (post-Baseline), T2 lesion volume, new unenhancing T1 lesion number, T1 unenhancing lesion volume) by visit/time
- Brain volume loss (BVL) assessment (whole brain and regional) (also obtained in HC for normalization purpose) by visit/time

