**Table 1 Study objectives and endpoints**

Objective(s)	Endpoint(s)

Primary Objective(s)
 
 
The primary objective is to explore the impact of ofatumumab on the ability to achieve No Evidence of Disease Activity (NEDA-3) status in treatment-naïve, very early RRMS participants over an 18 month, open-label study period after a re-baseline of MRI at 6 months
 
	
Endpoint(s) for primary objective(s)
 
 
NEDA-3 (relapse-free, 3-month clinical disability progression-free, MRI activity-free) in Months 6 to 18 (yes/no)
 

Secondary Objective(s)
 
 
Evaluate the effect of ofatumumab on various clinical (NEDA, disability, relapse) metrics at 18 months
 
Evaluate the effect of ofatumumab on conventional MRI metrics, with MRIs at Baseline and Months 6, 12, 18, 30 (T1 gadolinium (Gd) @ Baseline, Month 6, 18 and T1/T2 @ every timepoint)
 
Evaluate the effect of ofatumumab on patient reported outcomes (PROs) (Quality of Life in Neurological Disorders [NeuroQOLTM], Patient Determined Disease Steps [PDDS])
 
Evaluate the effect of ofatumumab vs healthy controls on 1) whole brain and regional atrophy measured at Month 18/30 after re-baseline at 6 months; and 2) regional atrophy measured 18/30 months from Baseline
 
Evaluate the safety and tolerability of ofatumumab
 
	
Endpoint(s) for secondary objective(s)
 
 
Number of confirmed relapses in Months 6 to 18
 
3-month disability worsening-free in Months 6 to 18 (yes/no)
 
NEDA clinical in Months 6 to 18 (yes/no)
 
NEDA radiological in Months 6 to 18 (yes/no)
 
Change from baseline in conventional MRI metrics (Gd+ lesion number, new Gd+ lesion number, Gd+ lesion volume, T2 lesion number (Baseline), new/enlarging T2 lesion number (post-Baseline), T2 lesion volume, new/enlarging T2 lesion volume, new unenhancing T1 lesion number, T1 unenhancing lesion volume)
 
Change from baseline in PROs (NeuroQOLTM, PDDS) (also obtained in healthy controls)
 
Brain volume assessment (whole brain and regional) (also obtained in healthy controls)
 
Adverse events, laboratory data, physical examination, and vital signs (also obtained in healthy controls)
 

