### 1.2.1 Primary estimand(s)

The estimand is the precise description of the treatment effect and reflects strategies to address events occurring during the trial conduct which could impact the interpretation of the trial results (e.g., premature discontinuation of treatment).

The primary clinical question of interest is: will treatment with ofatumumab allow young and very early RRMS patients to achieve NEDA-3 at 18 months?

The justification for the primary estimand is that it will capture the effect of ofatumumab on shutting down MS inflammatory and associated clinical disease activity within the central nervous system (CNS) in a RRMS population that is at first diagnosis.

The primary estimand is described by the following attributes:

- **Population:** Defined through appropriate inclusion/exclusion criteria to reflect the targeted population. Young adult and very early RRMS (defined as within 6 months of diagnosis of clinically definite RRMS) patients that are DMT treatment naïve.
- **Variable:** NEDA-3 (relapse-free, clinical disability progression-free, MRI activity-free) in Months 6 to 18 (yes/no)
- **Treatment of interest:** An initial dose regimen consisting of doses administered at Baseline/Week 0 (Day 1), followed by Week 1 (Day 7), Week 2 (Day 14), and then every month thereafter, beginning at Week 4 (Month 1) until Month 18 (see [Figure 1](#)). All doses of ofatumumab will be given subcutaneously via an auto-injector at a dose of 20 mg. Healthy controls will be used for comparison purposes and will not receive study treatment.
- **Intercurrent event:** Treatment discontinuation due to lack of efficacy or death

- **Summary measure:** Proportion of participants achieving NEDA-3 in Months 6 to 18

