### 2.5.1 Primary endpoint(s)

The primary endpoint is NEDA-3 (relapse-free, 3-month clinical disability progression-free, MRI activity-free) in Months 6 to 18 (yes/no). The 3 components of the primary endpoint are defined as follows:

- Relapse-free is defined as no confirmed relapses. Partial relapse start and end dates will be imputed as outlined in [Section 5.1.3.3](#). Criteria for the linking/combining of individual relapses is outlined in [Section 5.1.3.4](#).
- 3-month clinical disability progression-free is defined as no clinical disability progression as measured by EDSS (global assessment scale), where 3-month confirmed clinical disability progression is defined as an increase from Month 6 in EDSS (global assessment scale) sustained for at least 3 months. That is, after a scheduled or unscheduled visit at which the participant fulfills the clinical disability progression criteria as outlined in [Table 7](#), all EDSS assessments (scheduled or unscheduled) need to also fulfill the clinical disability progression criteria until the progression can be confirmed at the first scheduled visit that occurs in the absence of relapse (confirmed or unconfirmed) 3 months after the onset of the progression, or later. If a participant fulfills the clinical disability progression criteria based on the single EDSS assessment at Month 18, it will be considered a confirmed clinical disability progression (sustainment for at least 3 months will not be required). If a participant dies due to MS (i.e., EDSS = 10 at any time), it will be considered a confirmed clinical disability progression regardless of the Month 6 EDSS or change in EDSS.

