**Table 7 Criteria for clinical disability progression based on change from Month 6 in EDSS (global assessment scale)**

EDSS at Month 6	Clinical disability progression criterion
0	≥ +1.5
1 to 5	≥ +1
≥5.5	≥ +0.5

- MRI activity-free is defined as no Gd+ lesions on any MRI scan (scheduled or unscheduled) after Month 6, or new/enlarging T2 lesions compared to Month 6 on any MRI scan (scheduled or unscheduled) after Month 6.

The primary estimand is described by the following attributes:

- **Population:** Defined through appropriate inclusion/exclusion criteria to reflect the targeted population. Young adult and very early RRMS (defined as within 6 months of diagnosis of clinically definite RRMS) patients that are DMT treatment naïve.

- **Variable:** NEDA-3 (relapse-free, clinical disability progression-free, MRI activity-free) in Months 6 to 18 (yes/no)
- **Treatment of interest:** An initial dose regimen consisting of doses administered at Baseline/Week 0 (Day 1), followed by Week 1 (Day 7), Week 2 (Day 14), and then every month thereafter, beginning at Week 4 (Month 1) until Month 18. All doses of ofatumumab will be given subcutaneously via an auto-injector at a dose of 20 mg. Healthy controls will be used for comparison purposes and will not receive study treatment.
- **Intercurrent event:** Treatment discontinuation due to lack of efficacy or death
- **Summary measure:** Proportion of participants achieving NEDA-3 in Months 6 to 18

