The number of new/enlarging T2 lesions in Months 6 to 18 for each participant = Month 12 value (i.e., Month 12 scan relative to Month 6 scan) + Month 18 value (i.e., Month 18 scan relative to Month 12 scan). Participants are excluded from this calculation if the Month 6 value

(i.e., Month 6 scan relative to baseline scan) is missing. Only participants with a Month 6 value and at least one of the Month 12 or Month 18 values are included in this calculation.

The annualized new/enlarging T2 lesion rate (participant-based) will be summarized descriptively as a continuous variable by Cohort using the FAS or HCAS, as appropriate. The annualized new/enlarging T2 lesion rate (cohort-based), along with its components (i.e., numerator and denominator), will be reported by Cohort using the FAS or HCAS, as appropriate.

The annualized relapse rate (ARR) will be calculated using a participant-based approach and a cohort-based approach as follows:

- **Participant-based approach:**  $[(\text{number of confirmed relapses in Months 6 to 18 for a given ofatumumab-treated participant}) / (\text{number of days in Months 6 to 18 for a given ofatumumab-treated participant})] \times 365.25$
- **Cohort-based approach:**  $[(\text{total number of confirmed relapses in Months 6 to 18 for all participants within the ofatumumab-treated cohort}) / (\text{total number of days in Months 6 to 18 for all participants within the ofatumumab-treated cohort})] \times 365.25$

The ARR (participant-based) will be summarized descriptively as a continuous variable using the FAS. The ARR (cohort-based), along with its components (i.e., numerator and denominator), will be reported using the FAS. The ARR (both participant- and cohort-based) will also be derived through Month 18 and summarized descriptively using the FAS.

The number and percentage of participants with 0, 1, 2 or  $\geq 3$  confirmed relapses in Months 6 to 18 will be presented using the FAS. In addition, the number and percentage of participants with at least 1 confirmed relapse in Months 6 to 18 will be presented using the FAS. Participants with confirmed relapses through Month 18 will be summarized in a similar manner using the FAS.

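### The SAP narrows the protocol's whole-study disability endpoint to Months 6 to 18 and measures it from Month 6 EDSS, so no visible EDSS analysis runs from first dose to Month 18

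*SAP*

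**What the plan says.** **Protocol.** Section 12.5.1 lists the secondary endpoint "3-month disability worsening-free (yes/no) during the study". In the same list the two NEDA items carry a Months 6 to 18 window, so the protocol gives disability a different window from NEDA. The re-baselining statement in section 3 concerns imaging: "MRI data will be re-baselined at month 6 to account for treatment-related pseudo atrophy". No EDSS reference visit appears in the visible protocol text.

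**SAP.** Table 1 keeps the objective as "Evaluate the effect of ofatumumab on various clinical (NEDA, disability, relapse) metrics at 18 months". Sections 1.2, 2.6.1 and 2.6.2 restrict the disability endpoint to Months 6 to 18, analysed among completers in the FAS. The definition in 2.5.1 is "defined as an increase from Month 6 in EDSS (global assessment scale) sustained for at least 3 months", and Table 7 sets the thresholds by Month 6 EDSS. No separate definition is given for the secondary endpoint, so I take 2.5.1 to govern it.

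For relapses the SAP adds a longer view in 2.6.2: "Participants with confirmed relapses through Month 18 will be summarized in a similar manner using the FAS". The annualized relapse rate is also derived through Month 18. Section 4 reports the Months 6 to 18 window for relapses and disability together, as a clarification.

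**The concern.** Two things changed together. The window lost its first six months, and the reference moved from before treatment to six months into treatment. The protocol's reason for re-baselining, pseudo-atrophy, concerns brain volume and gives no ground for resetting a clinical disability score.

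The protocol gave relapses and disability the same whole-study scope, and the SAP narrowed both. It then restored the longer view for relapses only. The planned disability result thus describes 12 months on treatment relative to a mid-treatment value, while the objective speaks of 18 months. A reader could not tell from it how many participants are worse at Month 18 than when they started.

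**Working it through.** **The plan's own figures.** The plan states no expected rate or precision for the disability endpoint. Its only precision figures are for NEDA-3 (Protocol 12.8.1, SAP 3.1), and they reproduce:
- At 80%: 1.96 × √(0.80 × 0.20 / 100) = 7.84 points.
- At 85%: 1.96 × √(0.85 × 0.15 / 100) = 7.00 points.
- Enrolment: 100 / 0.85 = 117.6, so 118.

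They serve below only as a yardstick.

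**Effect of the reference visit.** Table 7 requires a rise of at least 1.5 from a reference of 0, at least 1 from a reference of 1 to 5, and at least 0.5 from 5.5 upward. I applied it to invented EDSS paths whose entry values lie in the eligible range of 0 to 3.0:

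| Entry, M6, M12, M18 | Measured from entry | Measured from Month 6 |
|---|---|---|
| 2, 3, 3, 3 | +1 at M6, held at M12: worsened | 0: worsening-free |
| 1, 2, 2, 2 | +1 at M6, held at M12: worsened | 0: worsening-free |
| 0, 1.5, 1.5, 1.5 | +1.5 at M6, held at M12: worsened | 0: worsening-free |
| 2, 2.5, 3, 3 | +1 at M12, held at M18: worsened | +0.5, needs +1: worsening-free |
| 3, 1.5, 2.5, 2.5 | −0.5: not worsened | +1 at M12, held at M18: worsened |
| 2, 2, 3, 3 | +1 at M12, held at M18: worsened | +1 at M12, held at M18: worsened |

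In the first three rows the criterion is met by Month 6, so the narrower window alone might exclude them. The fourth row isolates the reference: from entry the criterion is first met at Month 12, inside the window, yet the Month 6 reference removes it. The fifth row shows the opposite error. The last row shows no difference when EDSS is stable to Month 6.

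The opposite error is easier at the final visit, because 2.5.1 accepts a single qualifying Month 18 value without three months of sustainment. A participant at 2.5 on entry, 1.0 at Months 6 and 12 and 2.0 at Month 18 counts as progressed (+1.0), although 0.5 better than at entry.

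**Size.** Per 100 participants analysed, let *a* be worsening-free from Month 6 but worsened from entry, and *b* the reverse. The Months 6 to 18 proportion then exceeds the entry-referenced proportion by *a* − *b* points. The documents give neither number. Purely as assumptions, *a* − *b* of 1, 3, 5 or 10 makes the planned figure 1, 3, 5 or 10 points more favourable, and −1 or −3 makes it 1 or 3 points less favourable. A net 7 or 8 would equal the half-width planned for NEDA-3.

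**Are the data there?** EDSS is required at screening and baseline (Protocol 5.1, criterion 7). SAP Table 3 has EDSS windows at baseline, Weeks 1, 2 and 4, and Months 3, 6, 12 and 18. Worsening first seen at Month 3 (day 90) can be confirmed at Month 6 (day 180).

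**The case against.** **The Months 6 to 18 window for NEDA-3 is the protocol's own.** This stands. It appears in Protocol Table 2-1, 2.1 and 12.4.1, and nothing here faults it.

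**The SAP fills a gap.** No EDSS reference is visible in the protocol, parts of the efficacy section are blacked out, and the start of the window is a natural reference for progression within it. For NEDA-3 this stands: the Month 6 reference is an unlisted choice, not a contradiction. It does not carry over to the secondary endpoint, whose protocol window opens with the study.

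**The window change is disclosed.** It is, in SAP section 4. But replacing a whole-study window with a 12-month one changes the endpoint, and the new EDSS reference is not in the visible list.

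**Other analyses may cover the gap.** Table 3 suggests by-visit EDSS summaries, which may sit in blacked-out SAP text. PDDS is summarised as change from baseline (2.10). By-visit scores would not give a count of confirmed worsening, and PDDS is self-rated and serves the patient-reported objective. What stands is that the gap can be asserted for visible text only.

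**A stronger reading.** A reader might infer that early clinical failures are forgiven and that NEDA-3 is therefore several points too favourable. At the protocol's on-treatment relapse rates of 0.10 and 0.11 per year, 1 − exp(−0.5 × rate) gives 4.9% and 5.4% with a relapse in the first half-year, or 5.8 and 6.3 of 118. The documents do not support counting these as an error: leaving them out of NEDA-3 follows the protocol's window, and the through-Month-18 summaries already report them. Nor can they be added to an early-worsening share, because no such share is given and the two groups may overlap.

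**Conclusion.** The point holds for the secondary disability endpoint. The protocol specified whole-study disability worsening. The SAP replaces it with worsening over Months 6 to 18 from a Month 6 reference, and no visible EDSS-based analysis covers first dose to Month 18.

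The size and sign of the effect cannot be determined. Persistent early worsening makes the planned figure too favourable; improvement by Month 6 followed by partial loss makes it too strict. Improvement is plausible in a population within 6 months of diagnosis, whose relapses may have been treated before entry. A claim of one-directional bias would go beyond the documents.

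The conclusion assumes that the definition in 2.5.1 applies to the secondary endpoint and that blacked-out text holds no confirmed-worsening analysis from baseline. I read the protocol's whole-study scope as first dose to Month 18 for the primary analysis, because the objective names 18 months and Protocol 12.7 plans no estimation at Month 30.

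**What to change.** 1. Keep the Month 6 EDSS reference and the Months 6 to 18 window for NEDA-3.
2. In SAP 2.6.1 and 2.6.2, add 3-month confirmed disability worsening from pre-treatment baseline EDSS through Month 18, beside the existing through-Month-18 relapse summary. Report number, percentage and exact 95% CI in the FAS, with the denominator stated. Use the Table 7 thresholds and the 2.5.1 confirmation rules, read against baseline EDSS, so that the two disability tables differ only in reference and window.
3. In SAP section 4, list the Month 6 EDSS reference and the narrowed disability window as changes from the protocol, with a reason for each.

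The cost is one extra table and a few lines of SAP text; no new visits, data or participants are needed. The added figure may be less favourable than the Months 6 to 18 version.

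A supplementary NEDA-3 with clinical components counted from first dose, or a title that spells out the 12-month period, would be optional and is not needed to settle this point.

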**Table 7 Criteria for clinical disability progression based on change from Month 6 in EDSS (global assessment scale)**

EDSS at Month 6	Clinical disability progression criterion
0	≥ +1.5
1 to 5	≥ +1
≥5.5	≥ +0.5

- MRI activity-free is defined as no Gd+ lesions on any MRI scan (scheduled or unscheduled) after Month 6, or new/enlarging T2 lesions compared to Month 6 on any MRI scan (scheduled or unscheduled) after Month 6.

The primary estimand is described by the following attributes:

- **Population:** Defined through appropriate inclusion/exclusion criteria to reflect the targeted population. Young adult and very early RRMS (defined as within 6 months of diagnosis of clinically definite RRMS) patients that are DMT treatment naïve.

- **Variable:** NEDA-3 (relapse-free, clinical disability progression-free, MRI activity-free) in Months 6 to 18 (yes/no)
- **Treatment of interest:** An initial dose regimen consisting of doses administered at Baseline/Week 0 (Day 1), followed by Week 1 (Day 7), Week 2 (Day 14), and then every month thereafter, beginning at Week 4 (Month 1) until Month 18. All doses of ofatumumab will be given subcutaneously via an auto-injector at a dose of 20 mg. Healthy controls will be used for comparison purposes and will not receive study treatment.
- **Intercurrent event:** Treatment discontinuation due to lack of efficacy or death
- **Summary measure:** Proportion of participants achieving NEDA-3 in Months 6 to 18

### 2.5.2 Statistical hypothesis, model, and method of analysis

The number and percentage of participants achieving NEDA-3 in Months 6 to 18 will be presented using the mFAS. The 2-sided 95% CI for the proportion of participants achieving NEDA-3 in Months 6 to 18 will be calculated using an exact method (Clopper and Pearson, 1934).

### 2.5.3 Handling of intercurrent events

Handling of treatment discontinuations will follow composite variable strategy. For treatment discontinuation prior to Month 18 due to lack of efficacy or death, NEDA-3 and associated endpoints will be considered as “non-response”; if treatment discontinuation prior to Month 18 is due to reasons other than lack of efficacy or death, or if the Month 18 visit was completed but relapse/EDSS/MRI (Gd+ or new/enlarging T2 lesions) was missed at Month 6, 12 or 18, and disease activity was not shown (i.e., MRI activity after Month 6 through 18 or relapse/3-month clinical disability progression between Months 6 and 18), the participant will be excluded from mFAS for all NEDA-3 and associated endpoints efficacy analyses and thusly out of scope for intercurrent events handling; the rest of the participants had disease activities in Months 6 to 18, and NEDA-3 and associated endpoints for those participants will be considered as “non-response”.

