## 2.2 Analysis sets

The Full Analysis Set (FAS) will include all enrolled participants that received any study drug.

The Safety Analysis Set (SAF) will be the same as the FAS.

The Healthy Control Analysis Set (HCAS) will include all enrolled healthy control participants. This analysis set will be used in the analysis of data collected from healthy control participants.

The modified FAS (mFAS) will include all participants in the FAS except for those who discontinued treatment prematurely prior to Month 18 for reasons other than lack of efficacy or death, or those who completed their Month 18 visit but missed relapse/EDSS/MRI (Gd+ or

new/enlarging T2 lesions) at Month 6, 12 or 18, unless they showed disease activity (i.e., MRI activity after Month 6 through 18 or relapse/3-month clinical disability progression between Months 6 and 18). The mFAS will be used for NEDA-3, NEDA clinical and NEDA radiological efficacy analyses.

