### 2.5.4 Handling of missing values not related to intercurrent event

If treatment discontinuation prior to Month 18 is due to reasons other than lack of efficacy or death, or if the Month 18 visit was completed but relapse/EDSS/MRI (Gd+ or new/enlarging T2 lesions) was missed at Month 6, 12 or 18, and disease activity was not shown (i.e., MRI activity after Month 6 through 18 or relapse/3-month clinical disability progression between Months 6 and 18), the participant will be excluded from mFAS for all NEDA-3 and associated endpoints efficacy analyses and thusly out of scope for intercurrent events handling.

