### 2.6.1 Secondary endpoint(s)

Secondary efficacy endpoints include the following:

- Number of confirmed relapses in Months 6 to 18
- 3-month disability worsening-free in Months 6 to 18 (yes/no)
- NEDA clinical (relapse-free, 3-month clinical disability progression-free) in Months 6 to 18 (yes/no)
- NEDA radiological (MRI activity-free) in Months 6 to 18 (yes/no) for ofatumumab-treated participants, where MRI activity-free is defined as no Gd+ lesions on any MRI scan (scheduled or unscheduled) after Month 6, or new/enlarging T2 lesions compared to Month 6 on any MRI scan (scheduled or unscheduled) after Month 6
- NEDA radiological (MRI activity-free) in Months 6 to 18 (yes/no) for ofatumumab-treated and healthy control participants, where MRI activity-free is defined as no new/enlarging T2 lesions compared to Month 6 on any MRI scan (scheduled or unscheduled) after Month 6
- Change from baseline, as well as change from Month 6 re-baseline, in the following conventional MRI metrics by time point: Gd+ lesion number, Gd+ lesion volume, T2 lesion volume and T1 unenhancing lesion volume
- Values of the following conventional MRI metrics by time point (baseline or post-baseline, as appropriate): new Gd+ lesion number, T2 lesion number, new/enlarging T2 lesion number, new unenhancing T1 lesion number and new/enlarging T2 lesion volume

- Percent change from baseline and percent change from Month 6 re-baseline in brain volume parameters (whole brain and regional) by time point (also obtained in healthy control participants for normalization purposes)

Note that Gd will not be given to healthy control participants and Gd enhanced T1 MRI imaging will not be conducted in healthy control participants.

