The number and percentage of participants achieving 3-month disability worsening-free in Months 6 to 18 will be presented using an observed case approach (completers) using the FAS. The number and percentage of participants achieving NEDA clinical in Months 6 to 18 and NEDA radiological in Months 6 to 18 using the ofatumumab-treated participants derivation described in [Section 2.6.1](#) will be presented using the mFAS. In addition, the number and percentage of participants achieving NEDA radiological in Months 6 to 18 using the ofatumumab-treated and healthy control participants derivation described in [Section 2.6.1](#) will be presented using the mFAS or HCAS, as appropriate. The 2-sided 95% CI for the proportion of participants achieving each of these endpoints will be calculated using an exact method ([Clopper and Pearson, 1934](#)).

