### **2.6.3 Handling of intercurrent events**

For NEDA clinical in Months 6 to 18 and NEDA radiological in Months 6 to 18, the same approach outlined for NEDA-3 in [Section 2.5.3](#) will be followed. For all other secondary endpoints, there is no imputation of missing data planned for this study.

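### The NEDA-3 missed-item rule is carried over unchanged to NEDA clinical and NEDA radiological, so participants leave those endpoints because of items the endpoints do not use

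*SAP*

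**What the plan says.** SAP Section 2.2 defines one mFAS for NEDA-3, NEDA clinical and NEDA radiological. Participants who completed Month 18 but lack a relapse, EDSS or MRI item at Month 6, 12 or 18 are left out, "unless they showed disease activity (i.e., MRI activity after Month 6 through 18 or relapse/3-month clinical disability progression between Months 6 and 18").

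Section 2.5.3 repeats the rule: exclusion applies "or if the Month 18 visit was completed but relapse/EDSS/MRI (Gd+ or new/enlarging T2 lesions) was missed at Month 6, 12 or 18" and no activity was shown. For those who are kept, "NEDA-3 and associated endpoints for those participants will be considered as" non-response. Section 2.5.4 says that, in the same situation, "the participant will be excluded from mFAS for all NEDA-3 and associated endpoints efficacy analyses".

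Section 2.6.1 lists "NEDA clinical (relapse-free, 3-month clinical disability progression-free) in Months 6 to 18 (yes/no") and defines NEDA radiological by MRI alone. Section 2.6.3 then states: "For NEDA clinical in Months 6 to 18 and NEDA radiological in Months 6 to 18, the same approach outlined for NEDA-3 in" Section 2.5.3 applies. Section 2.6.4 says the same with reference to Section 2.5.4.

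Section 2.6.2 analyses NEDA clinical and NEDA radiological in the mFAS. The T2-only version of NEDA radiological, shared with healthy controls, "will be presented using the mFAS or HCAS, as appropriate". The HCAS is all enrolled controls (Section 2.2). Section 2.6.6 plans no supplementary analysis of secondary endpoints.

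**The concern.** For NEDA-3 the rule has a logic. One observed event settles failure, and no event with a missing component leaves the status unknown. That logic does not carry over to an endpoint that does not use the missing component. For NEDA clinical, a participant with complete relapse and EDSS data has a known status whatever happened to the scan. Dropping that participant when the status is success, and keeping the counterpart when any activity is seen, makes inclusion depend on the outcome for no gain in information.

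At stake are two secondary proportions and, for the T2-only version of NEDA radiological, a display beside controls whose analysis set has no matching rule.

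**Working it through.** **The same gap followed through the text.** Take Month 18 completers with full relapse and EDSS data who missed only the Month 12 MRI:

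| Participant | True NEDA clinical status | Treatment under the SAP |
|---|---|---|
| No activity | Success, fully observed | Excluded |
| MRI activity only (seen on another scan) | Success | Kept; success by own components, failure if Section 2.5.3 is read literally |
| Relapse or progression | Failure | Kept as failure |

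For NEDA radiological, a participant with all scans, no activity and a missed Month 12 EDSS is excluded although the endpoint is fully observed.

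**Plan's own figures** (Section 3.1). 1.96 × √(0.80 × 0.20/100) = 7.84% and 1.96 × √(0.85 × 0.15/100) = 7.00%; 100/0.85 = 117.6, so 118. All three reproduce.

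**Inputs.** p = NEDA-3 rate, 0.80 or 0.85 (Section 3.1). pc = NEDA clinical rate, 0.90 to 0.95 (assumed). m = share missing only the Month 12 MRI, 0.02 to 0.10 (assumed; the documents give no rate, and the low end fits a reading in which nothing falls in the day 271 to 450 window). Missingness is taken as unrelated to outcome, and MRI activity as still visible on other scans.

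**NEDA clinical, scored on its own components.** Expected estimate = [(1−m)pc + m(pc−p)] / [(1−m) + m(1−p)].
- m = 0.02, p = 0.80, pc = 0.95: (0.931 + 0.003)/0.984 = 0.9492, shift -0.1 points.
- m = 0.05, p = 0.85, pc = 0.90: (0.855 + 0.0025)/0.9575 = 0.8956, shift -0.4.
- m = 0.10, p = 0.85, pc = 0.90: (0.81 + 0.005)/0.915 = 0.8907, shift -0.9.

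Over the whole grid the range is -0.1 to -0.9. If none of the MRI activity were visible, the formula becomes (1−m)pc / [(1−m) + m(1−pc)]; its worst case is 0.81/0.91 = 0.8901, shift -1.0. Visibility therefore matters little here.

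**NEDA clinical, Section 2.5.3 read literally** (every kept incomplete participant fails). Expected estimate = pc(1−m) / [(1−m) + m(1−p)].
- m = 0.02: -0.3 to -0.4 points.
- m = 0.10, p = 0.80, pc = 0.95: 0.855/0.92 = 0.9293, shift -2.1, the largest on the grid.

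**Yardstick.** The exact 95% half-width is 6.4 points at 90/100 and 4.8 at 95/100 (Clopper-Pearson).

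**NEDA-3, for context.** With d the share of activity visible without Month 12, estimate = p(1−m) / [(1−m) + (1−p)md].
- d = 1: -0.3 at m = 0.02; -0.7 to -1.7 at m = 0.05 to 0.10.
- d = 0.5, m = 0.05 to 0.10: -0.3 to -0.9.
- If missers have only 50% NEDA-3 and half their activity is visible, the sign reverses: +0.5 to +1.2.

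Exact half-widths at n = 100 are 7.4 (85%) and 8.3 (80%).

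**The case against.** The strongest reply is that the effect is small, rests on assumed missing rates and touches descriptive results only, since no hypothesis is tested (Section 5.4). That stands and limits the weight of the point. It does not rescue the rule, because the misclassification follows from the text whatever the rates.

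A reader might go further in four ways that the documents do not support.

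- *The primary NEDA-3 rule should be replaced.* Ignoring a missed Month 12 item would miss activity seen only then. With missingness unrelated to outcome, it has the smaller bias only if more than about 52-55% of activity is visible without Month 12, or 87-91% if missers have 50% NEDA-3. The documents give no such share. A carve-out for progression awaiting confirmation would not remove outcome dependence either: a rise must persist "until the progression can be confirmed at the first scheduled visit that occurs in the absence of relapse" at least three months on, so Month 18 can confirm it, and those it confirms would stay while the others left. Section 2.5.6 already plans an observed-case analysis needing only the Month 6 and Month 18 visits.
- *Section 2.5.3 certainly fails participants with MRI activity only on NEDA clinical.* It can be read so. But its closing clause, taken literally, would also make complete, activity-free participants non-responders, which cannot be meant. The -2.1 is therefore an upper end, not the expected effect.
- *Gd is required at Month 12.* The bracket joins Gd and T2 by an or, and Table 1 schedules no Gd at Month 12; an unscheduled item is not naturally a missed one.
- *The T2 reference scans conflict.* Section 2.5.1 fixes Month 6 for NEDA; the Month 12 reference in Section 2.6.2 belongs to the annualized lesion rate.

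**Conclusion.** Sections 2.6.3 and 2.6.4, together with the single mFAS, are wrong as written for NEDA clinical and NEDA radiological: observed successes are dropped for items that those endpoints do not use. The likely shift in NEDA clinical is about -0.1 to -0.9 points on its own components, and up to about -2.1 if Section 2.5.3 is applied literally. Both are below the interval half-width. They rest on assumed values: 2-10% missing only the Month 12 MRI, a 90-95% true rate, missingness unrelated to outcome and activity still visible. No figure can be given for NEDA radiological or its display beside controls. It is worth correcting because the text gives a wrong classification, no other planned analysis would show it, and correction needs only wording.

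For NEDA-3, keeping known failures and dropping unknown statuses is a defensible choice. It can pull the proportion slightly down; the direction is not certain.

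**What to change.** Before the Month 18 database lock:

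1. In Sections 2.2, 2.6.3 and 2.6.4, define evaluability for NEDA clinical by relapse and EDSS only, and for NEDA radiological by MRI only.
2. State that each endpoint is scored on its own components, so that the non-response clause in Section 2.5.3 cannot be read across endpoints.
3. For the T2-only NEDA radiological derivation, apply the same missed-scan rule to healthy controls as to treated participants.
4. For NEDA-3, keep the planned rule. Report how many participants with incomplete data were excluded and how many were kept as failures, and present the result beside the observed-case analysis of Section 2.5.6.

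The cost is SAP wording, programming of endpoint-specific flags and a few counts; no new visits or scans. The downside is that NEDA clinical and NEDA radiological may have slightly different denominators from NEDA-3. The plan already accepts this for 3-month disability worsening-free, which Section 2.6.2 analyses by observed case in the FAS.
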